1. Referrals from VA health providers, including primary care providers, geriatricians, endocrinologists, and other subspecialist who care for diabetic patients.
2. Direct advertisement through local newspaper and at the VA for potential subjects.
3. Referrals from the VA Ann Arbor MOVE! program. The MOVE! program in VA Ann Arbor provided care for 710 veterans in 2010, with 490 of them as first time participants in MOVE! program;⁶¹ 50% of the MOVE! participants have diabetes.⁶²
4. We will obtain VA Institutional Review Board's approval to screen for diabetic patients using the VA electronic medical record. After identifying potential subjects, we will contact their primary providers for approval to recruit these patients.

Sample:

[figure not shown]
We will recruit approximately 70 veterans who have known diabetes and are aged ≥ 60 years. Subjects will be recruited based on their self-reported diabetes diagnosis. After identifying potential subjects, we will send them introductory letters describing the study, including an opt-out postcard for them to mail back. If we do not receive the opt-out postcard after 2 weeks, then we will contact the veterans by phone to confirm their interest in participating in the study and to screen for eligibility.

Eligibility

Inclusion Criteria

- Aged ≥ 60 years
- Diagnosis of diabetes mellitus, type 2 (or adult-onset) (self-reported or per medical record)
- At least 5/6 on 6-item cognitive screening test on the phone
- Ability to reliably operate the Actiwatch accelerometer
- Community-living (i.e., not nursing home resident)
- Ambulatory either with or without an assistive device
- English-speaking
- Competent to provide informed consent
- Sedentary (< 150 min moderate activity in a week)

Figure 3.

Exclusion Criteria

- Medically unstable in which exercise would be contraindicated (e.g., previous severe symptomatic hypoglycemia, decompensated congestive heart failure, severe anemia, severe aortic stenosis, unmanaged thyroid dysfunction, etc.)
- Self-reported illness or conditions that impair cooperation with the study team or ability to complete study procedures
- Hospitalization within last 6 months for any reason
- 2 or more days of complete bed rest within the last month
- Limb hemiplegia or amputation
- Replacement of any hip or knee joint within the last 6 months
- Current attendance in a PA program
- Work involves shift schedule
- Heart attack within past month
- Parkinson's disease

PARTICIPANT TIMELINE

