1. The Six- Minute Walk Test⁶⁴ – A participant will be instructed to walk at his/her usual pace for six minutes and distance covered in feet is recorded.
2. Timed Up and Go Test⁶⁵ – A participant will be timed (in seconds) when get up from sitting in a chair, walk 3 meters, turn around, and walk back to sit down.
3. Comfortable gait speed in 10 meter walking.
4. Rosow, Breslau and Nagi activities⁸¹⁻⁸⁴ – Self-reported ability to run a mile, walk 1 or several blocks, sit for 2 hours, get up from a chair after sitting for a while, climb 1 or several flights of stairs, lift or carry over 10 lbs., stooping/crouching/kneeling, pick a dime up, reach or extend arms, and pulling/pushing large objects.

b) **Biomarkers:** A1c and body mass index will be assessed at baseline and at the final (or 6-month) follow-up. A1c measures average blood glucose level in the past 3 months. At the time when participants visit VA Ann Arbor for baseline and final assessment, they will be asked to go to the VA Ann Arbor's Ambulatory Care laboratory to have a random blood sample obtained by the staff to assess for A1c value. Standard scales used in Ambulatory care clinics will be used to measure the height and weight of each participant.

c) **Quality of life** will be assessed by VR-12, which is a well validated 12-item questionnaire that assesses both the physical and mental health quality of life of veterans.

d) **Participant retention** is the extent to which our program is able to retain the intended audience to complete the study.⁸⁶ Results from participation retention provide information on the acceptance of the intervention by the veterans. Retention can be calculated as [(participants completing post intervention assessment/participants enrolled) x 100].

e) **Intervention feedback** is an important goal for this pilot trial. It will inform the PI if certain part of the intervention should be revised, added, or removed to improve the intervention for future trials and for dissemination. The information will be obtained in two ways at the end of the study:

1. Participant satisfaction with the program, including participant perception of usefulness of proposed intervention, will be measured by a series of Likert scale satisfaction items adapted from the measures used by Schron et al.⁸⁷ (See Appendix).

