 - c) Description of activities and the involved context (i.e., what, where, with whom) in 2-hour intervals will be recorded by each study participant in an accompanying logbook during the baseline 7-day home monitoring period. An example: 7-9pm on Saturday - dinner, at restaurant, with family. The logbook will provide more descriptive data on the environment and other activities that a participant engaged in a day.

This information will be used in the study for the sole purpose of generating tailored reports on individual environment-activity relationships over the week for the tailored activity intervention in Aim 2.

2. Potential confounders including age, race, sex, global health status, co-morbidities (Charlson Comorbidity Index⁸⁹), depression, attitudes and beliefs about PA and diabetes care will be assessed using validated questionnaires:

- Geriatric Depression Scale (GDS)⁹⁰ Short Form is a 15-item questionnaire to screen for depression. It has been extensively used in community, acute and long-term care settings. GDS has 92% sensitivity and 89% specificity when evaluated against diagnostic criteria. It will take 5-7 minutes to complete.

- Diabetes Care Profile (DCP)⁹¹ is a self-administered questionnaire that assesses the social and psychological factors related to diabetes and its treatment. The instrument contains 234 items and sixteen scales. To reduce participant burden, we selected subsets of questions from DCP to assess diabetes-related attitudes and PA barriers, which are important factors for the study. We estimate it will take 10-15 minutes to complete these subsets of questions.

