Hypothesis 2a: *At the end of 6 months, individuals in the intervention group will have increased PA compared to the control group.* PA is measured in 3 ways using Actiwatch and CHAMPS (Table 5), so three separate analyses will be done using each measure – Actiwatch daily average counts and weekly counts, and CHAMPS weekly measurement.

The primary analysis is based on comparing the 6-month change in PA between treatment group and control group by t-tests. To adjust for potential confounding, separate models of multivariate regression analyses will be conducted with each measure of PA as the dependent variable, randomization arm as a predictor, baseline PA as a covariate, and potential confounders including age, sex, diabetes status, and number and perception of environment barriers will be included in the model. Assuming that residuals from the model fit are normally distributed, the analysis is equivalent to a classical analysis of covariance. For data that does not fit a normal distribution, inverse, logarithmic or power transformations will be performed or generalized linear models (GLM) with Poisson or gamma error will be considered.

To further assess if the pattern of PA changed, i.e., whether the change in PA occurred across each day or just a few days in a week, we will graphically compare the daily average counts at 6-month follow-up for the intervention group with the control group (Figure 5). For example: If Y_{ij} = daily average counts at day_j over 7 days after intervention for subject i and j = 1 (d1), 2 (d2), ..., 7(d7), then we will try to fit the linear mixed model to test if the slopes of the two PA curves are the same and test for overall difference ($\beta_1 = 0$):

$$Y_{ij} = \beta_0 + \beta_1 * \text{intervention} + \beta_2 * \text{days} + \beta_3 * z + \epsilon_{ij}$$

With this small sample of 28-35 participants per treatment group, it is possible that the study may be underpowered to determine significant differences between groups. However, the results will provide essential information about the actual effect size of the treatment which will allow us to better estimate the sample size needed for a larger trial.

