Hypothesis 2b: At the end of 6 months, individuals in the intervention group will have improved social participation (ability to participate and satisfaction with participation). Social participation will be measured with the PROMIS questionnaires with a population mean of 50 and standard deviation of 10. The change in *social participation* will be compared between the treatment and control groups by t-tests, similar to the analysis plan described for *Hypothesis 2a*. Multivariate regression analyses will be conducted to evaluate confounding factors, with social participation as the dependent variable, randomization arm as a predictor, baseline social participation as a covariate. Potential confounders including age, sex, co-morbidities, and number and perception of environment barriers will be included in the model. Distribution of the residuals from model fit will be examined, and additional transformations and generalized linear models will be considered.

Additional analyses:

Further exploration of effects at each time points are of interest. Models will utilize outcome measurements at all time-points (baseline, 5 weeks, and 6 months). Different outcome measures and covariates can be evaluated. Repeated measure longitudinal models can be considered:

For example: **Outcome at 5 weeks and 6 months = BA + G + CF + G*TIME + CF*TIME,**

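### The adjusted physical activity regression for Hypothesis 2a names diabetes status, which on its plain meaning is the same in every participant, and does not name co-morbidities

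*Combined protocol and SAP*

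**What the plan says.** All references are to the combined protocol and SAP.

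- **Hypothesis 2a, main test.** "The primary analysis is based on comparing the 6-month change in PA between treatment group and control group by t-tests".
- **Hypothesis 2a, adjusted models.** A separate regression is planned for each PA measure (two from the Actiwatch, one from CHAMPS), with randomization arm and baseline PA. In addition, "potential confounders including age, sex, diabetes status, and number and perception of environment barriers will be included in the model".
- **Hypothesis 2b.** Social participation is also compared by t-tests, followed by a regression with arm and baseline value. Here, "Potential confounders including age, sex, co-morbidities, and number and perception of environment barriers will be included in the model".
- **Eligibility, Inclusion Criteria.** One criterion is "Diagnosis of diabetes mellitus, type 2 (or adult-onset) (self-reported or per medical record"). The Sample paragraph agrees: "We will recruit approximately 70 veterans who have known diabetes and are aged ≥ 60 years".
- **Co-variates, predictors and confounders.** The measured list begins "Potential confounders including age, race, sex, global health status, co-morbidities", with the Charlson index as the instrument. It has no variable called diabetes status.
- **Secondary analyses.** Age, sex and co-morbidities are the named adjusters.
- **Biomarkers.** "A1c and body mass index will be assessed at baseline and at the final (or 6-month) follow-up".

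The term diabetes status is not defined anywhere.

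**The concern.** A covariate can adjust a comparison only if it varies between participants. In a trial that enrols only people with diabetes, a diabetes indicator does not vary. The 2a model would then carry a named health-status adjustment with no effect, in the position where the 2b model has one that works.

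By the plan's own reasoning, co-morbidity bears on PA. The section on tailored lifestyle interventions argues that managing several diseases leaves little time for other activity, and the preliminary work uses co-morbidity to justify tailoring. Diabetes was a usable predictor in the preliminary osteoarthritis analysis because that cohort mixed 20 diabetic with 147 non-diabetic participants. This trial has no such mix.

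At stake is whether the adjusted PA estimates are adjusted for what the plan says. The plan intends the results to supply the effect size for sizing a larger trial, so this should be clear.

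**Working it through.** The plan gives no figure to reproduce on this point. The check compares the lists, then the algebra, then the possible size.

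**1. The lists side by side**

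| Place | Age, sex | Diabetes status | Co-morbidities | Environment barriers |
|---|---|---|---|---|
| Hypothesis 2a regression | yes | yes | not named | yes |
| Hypothesis 2b regression | yes | no | yes | yes |
| Measured confounders | yes | no | yes (Charlson) | listed separately |
| Secondary analyses | yes | no | yes | not named |

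The 2a list is the only one with diabetes status and the only one without co-morbidities.

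**2. The algebra**

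Write the 2a model as Y = b0 + b1·arm + b2·baseline PA + b3·age + b4·sex + b5·D + b6·number of barriers + b7·perception of barriers. If D is diabetes yes/no, then D = 1 for everyone. Only the sum b0 + b5 can be estimated, and b1 is the same with or without D.

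This was confirmed by least squares on one simulated data set at each size, 56 (28 per arm) and 70 (35 per arm). The reduced model had intercept, arm, baseline and age. The assumed coefficients were 0.5 for arm, 0.6 for baseline and −0.3 for co-morbidity, with residual SD 1.

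| n | Added term | Columns | Rank | Arm estimate | SE | Residual df |
|---|---|---|---|---|---|---|
| 56 | none | 4 | 4 | 0.567315 | 0.266062 | 52 |
| 56 | constant diabetes indicator | 5 | 4 | 0.567315 | 0.266062 | 52 |
| 56 | varying co-morbidity score | 5 | 5 | 0.600668 | 0.264854 | 51 |
| 70 | none | 4 | 4 | 0.286298 | 0.246334 | 66 |
| 70 | constant diabetes indicator | 5 | 4 | 0.286298 | 0.246334 | 66 |
| 70 | varying co-morbidity score | 5 | 5 | 0.287510 | 0.223446 | 65 |

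The constant changes nothing. A varying score changes both estimate and SE, but by amounts that depend on the assumed coefficients, so these rows do not predict the gain in this trial.

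**3. Chance imbalance, as context only**

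The SE of a standardized baseline difference is sqrt(2/n per arm).

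- 35 per arm: sqrt(2/35) = 0.239; 0.25/0.239 = 1.046; P(imbalance ≥ 0.25 SD either way) = 2 × (1 − Φ(1.046)) ≈ 0.30.
- 28 per arm: sqrt(2/28) = 0.267; 0.25/0.267 = 0.935; probability ≈ 0.35.

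This holds for any roughly normal covariate at this size. Its effect on the PA estimate depends on how strongly co-morbidity predicts 6-month PA given baseline PA, which the documents do not give. If the standardized partial coefficient is assumed to be 0.1 to 0.3, a 0.25 SD imbalance shifts the estimate by 0.25 × 0.1 = 0.025 to 0.25 × 0.3 = 0.075 SD. The SE of the comparison itself is about 0.24 SD at 35 per arm.

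**The case against.** **The term may mean something that varies.** It is undefined, and the trial records diabetes measures that differ between people: baseline A1c, glucose-lowering medication and diabetes-related attitudes. If one of these was meant, the term would not be void. This stands as a limit. But no section equates any of them with diabetes status, so the term would still need defining and co-morbidities would still be unnamed for 2a.

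**Co-morbidity is unlisted, not excluded.** The 2a list is introduced as open. Baseline comparisons cover all covariates, and the Additional analyses allow contributing factors for both hypotheses. A reader might infer that the plan rules co-morbidity out of the PA model; the text does not go that far. The Missing Data rule is a narrower route, since it adds baseline variables only when they are associated with loss to follow-up.

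**The main tests are untouched.** A reader might infer that the two primary outcomes are tested with different adjustment, or that a co-morbidity imbalance would go uncorrected for PA alone. Neither is right for the main tests: 2a and 2b both rest on unadjusted t-tests. The mismatch exists only between the supporting regressions.

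**The harm limits itself.** Randomization protects against systematic bias, and a constant column would show itself at the first model fit. Both points stand and keep the issue modest. They do not settle which variable the analyst should then use.

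**Conclusion.** The point holds for the supporting adjusted PA regressions. On the plain meaning of diabetes status, one named adjuster contributes no degrees of freedom and leaves the arm estimate and its SE unchanged, in all three PA models. Co-morbidity is not named there, in contrast to the 2b regression, the measured confounder list and the secondary-outcome models.

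The conclusion rests on reading diabetes status as presence or absence of diabetes. That is its ordinary sense, but the documents do not confirm it.

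The cost is limited to precision, control of chance imbalance and accurate description of the adjusted PA analyses, and the documents do not allow it to be quantified. The 30% to 35% chance of a 0.25 SD imbalance should not be read as a measure of bias in the PA effect. It is worth correcting because the correction is specific and cheap, but the main Hypothesis 2a test is not at risk.

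**What to change.** In the Hypothesis 2a paragraph, replace diabetes status with co-morbidities (Charlson Comorbidity Index), matching Hypothesis 2b.

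If diabetes severity was intended, name the baseline measure that varies, for example baseline A1c, and list co-morbidities as well.

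**Cost.** The first option changes one phrase, needs no new data and adds no term beyond the number already listed. A working covariate uses one residual degree of freedom that the constant did not. Counting one column per listed term, the full model without the void term has 7 columns (intercept, arm, baseline PA, age, sex, number of barriers, perception of barriers). Residual df then go from 56 − 7 = 49 to 48, or from 70 − 7 = 63 to 62. The second option costs one further degree of freedom (47 or 61). The t-tests do not change under either option.

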→ This study provides support for the proposed intervention to incorporate PA into an individual's daily life routines.

3. Diabetes is associated with poor mobility and less physical activity in symptomatic osteoarthritis patients ([name], [name], [name]; *Poster presented at the Annual Meeting of the Gerontological Society of America, 2013*)

We analyzed data from participants recruited for a life-style intervention trial by [name] group: community-living adults aged ≥ 65 years with mild to moderately painful knee or hip OA and fatigue. We assessed mobility by using Six-minute Walk distance (6MW; feet) and PA by using a wrist-worn accelerometer (Actiwatch) over 7 days (average count/day). Linear regression models were performed to examine the contribution of diabetes, age, body mass index, pain, and self-reported disability on mobility and on PA. We found that diabetic participants (n=20, mean age 72) were more obese than non-diabetic participants (n=147, mean age 72). Diabetic participants had shorter 6MW distance ($\beta = -131.87$, $p=0.03$), adjusting for age, BMI, pain and disability. They were less physically active, adjusting for age and BMI ($\beta = -55.78$, $p=0.03$).

→ Diabetes can be a barrier to PA among adults with OA, and adults with OA and diabetes need additional support to participate in PA. This study confirms that it's feasible to use Actiwatch to assess PA among older adults with diabetes, that these participants are able to use the Actiwatch and logbooks to record their momentary symptoms of fatigue and activities, which are key components of the proposed CDA. The acceptance of this study protocol among the participants also supports the proposed intervention.

4. Geriatric conditions, which are associated with physical disability, begin to develop in middle-aged adults with diabetes.⁵⁹

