The wrist-worn accelerometer will be mounted on each participant's non-dominant wrist. Although it is worn on the wrist, it is highly associated with whole-body movement.^{72,73} Changes in acceleration are recorded as activity counts and saved every 15 seconds. Higher activity counts reflect participation in higher intensity activities.^{74,75} Actiwatch has been shown to have excellent reliability between units ($r = .98$) and has established preliminary criterion validity among a sample of chronic pain patients.⁷⁶ Three main PA measurements are derived from the Actiwatch: 1) average activity counts/minute reflects average level of PA over a specified time period; 2) peak PA (largest daily activity count averaged over 7 days) is a measure of daily activity intensity; and 3) total PA is the 7-day cumulative activity score at times when a person was deemed awake and excluding missing data that occurred from temporary removal of the Actiwatch. We will look at average activity counts and total activity counts that occur: 1) in different context, 2) over each day, and 3) over the 7 day period. Because participants wear the accelerometer continuously for 7 days, it is necessary to establish participants' wake-up and bedtimes. A previously-established algorithm will be used to corroborate participant-report of wake and bedtimes with the objective measures.

2. Physical activity will also be self-reported by having the study participants completing the *Community Healthy Activities Model Program for Seniors (CHAMPS)* questionnaire.⁷¹ CHAMPS is a self-administered questionnaire developed for underactive populations and tested primarily among older adults. The questionnaire included 41 items, asking the respondent to report the participation in specific activities that older adults are likely to engage in. The responses are "YES" or "NO" to an activity, and if "YES", then the

number of times per week and total hours per week of activity participation. From the questionnaire, we can derive measures of frequency per week and estimated caloric expenditure per week in PA. For both frequency and caloric expenditure, two measures can be derived based on: 1) PA of moderate or greater intensity (MET value ≥ 3.0), and 2) all specified PA that included activities of light intensity in addition to moderate and greater. The 6-month reliability coefficients for total and moderate-intensity activities were 0.66 and 0.76, respectively.⁷¹

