Hypothesis 1: Lower levels of weekly and daily PA will be associated with a greater number of physical and social environmental barriers and less social participation.

Since PA is measured by Actiwatch objectively and self-reported by CHAMPS, we will first compare them with correlation analyses and identify the correlation coefficient. We will then use separate linear regression models to evaluate if environmental barriers (MQE) and social participation (PROMIS) predict PA, adjusting for baseline co-variates and potential confounders. Separate models will be used for the two different PA measurements - CHAMPS and Actiwatch.

Table 5.

Variables	Measures
PA(outcome)	Actiwatch – weekly and daily average counts
	CHAMPS – weekly energy expenditure (kcal/wk)
Environment	MQE – summary score of environment barriers/facilitators
	Momentary assessment – daily perception of environmental barrier (3 questions)
Social participation	PROMISE – summary score of participation ability and satisfaction
	Daily assessment – daily satisfaction with participation (3 questions)

We will then explore if the perception of environment barriers to PA and participation and satisfaction with participation fluctuate daily. Longitudinal analysis models will be built with time as covariate and each of these variables as the outcome. These variables are assessed daily during the home monitoring period by 6 separate questions adapted from validated questionnaires. We expect study participants' answers to some if not all of these questions to vary daily. We will

[figure not shown]
then build separate predictive models using hierarchical linear modeling (HLM) if change in the perception of the environment or satisfaction with participation is associated with PA (Actiwatch daily average counts). The HLMs will allow us to fully utilize the repeated measures of the environment, participation, and PA within each day.

Aim 2: To pilot a randomized-controlled trial to test the efficacy of an individually tailored lifestyle-based PA intervention. An intent-to-treat analysis will be applied to avoid various misleading artifacts that can arise in the trial; all subjects initially enrolled in the trial will be accounted for based on the group they were randomized into. Baseline comparison of the control and intervention groups will be done with ANOVA on PA, participation, and all the co-variates. We will consult our statistician for analysis guidance.

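### The covariate-adjusted PA regression lists a Poisson GLM, with no dispersion correction, among its options for non-normal data; uncorrected Poisson is invalid for all three PA measures

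*Combined protocol and SAP*

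**What the plan says.** In Statistical Analysis, Aim 2, Hypothesis 2a, the lead test is explicit: "The primary analysis is based on comparing the 6-month change in PA between treatment group and control group by t-tests". A second, adjusted analysis follows: "To adjust for potential confounding, separate models of multivariate regression analyses will be conducted with each measure of PA as the dependent variable", with randomization arm as predictor and baseline PA, age, sex, diabetes status and environmental barriers as covariates. For data that do not fit a normal distribution, the plan says that the outcome will be transformed (inverse, log or power) or that "generalized linear models (GLM) with Poisson or gamma error will be considered". It does not say which option applies when, and it attaches no dispersion estimate, quasi-likelihood or robust variance to the Poisson option.

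The outcomes are set out just before: "three separate analyses will be done using each measure – Actiwatch daily average counts and weekly counts, and CHAMPS weekly measurement". The Measures section describes the Actiwatch signal: "Changes in acceleration are recorded as activity counts and saved every 15 seconds". Table 5 expresses CHAMPS as weekly energy expenditure in kcal.

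**The concern.** Poisson error fixes the variance at the mean. That suits independent events counted one by one. An activity count is a digitised acceleration signal, and a kilocalorie total is a continuous quantity. For neither is there reason to expect the between-person variance to equal the mean in whatever unit was chosen. Where the variance is much larger, model-based Poisson standard errors are too small and p-values far too low.

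At stake is the adjusted PA result in a pilot whose stated purpose includes supplying an effect size for a larger trial. A falsely narrow interval around the adjusted effect, beside a non-significant t-test, could mislead that planning. The point is confined to Hypothesis 2a: the later sections also mention generalized linear models but do not name Poisson error.

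**Working it through.** The plan states no PA mean, SD, alpha or power, so there is no figure of its own to reproduce. Two-sided 5% is assumed throughout.

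**1. Dependence on the unit (no assumed mean needed).** Multiply the outcome by c. With a log link the estimated arm ratio is unchanged, but the Poisson model variance is divided by c, so z is multiplied by √c. Moving from a mean daily total to a seven-day total with complete wear gives c = 7 and √7 = 2.65. A z of 0.80 (p = 0.42) becomes 2.12 (p = 0.03) on the same data.

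**2. Size for average counts, without baseline adjustment.** True SE / Poisson SE = SD/√mean. A nominal 5% test then has type I error 2[1 − Φ(1.96/ratio)].

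An SD can be backed out of Preliminary Studies, item 3 (difference 55.78, p = 0.03, 20 diabetic and 147 non-diabetic participants, adjusted for age and BMI):
- df = 167 − 4 = 163, t = 2.189
- SE = 55.78/2.189 = 25.5
- SD = 25.5/√(1/20 + 1/147) = 107 (103 to 110 allowing for rounding of p)

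This ignores correlation between diabetes status and the covariates. For assumed means in the same unit:
- mean 100: ratio 10.7, type I error about 85%
- mean 300: ratio 6.2, 75%
- mean 1000: ratio 3.4, 56%

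The mean would have to exceed 107²/4, about 2,860, for the ratio to fall below 2.

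**3. Simulation with baseline adjustment, as the plan intends.** There was no true effect, with 28 or 35 per arm (the plan's range), lognormal outcomes, baseline correlation 0.6, log baseline as covariate and 600 replicates per scenario. Means, coefficients of variation (CV) and correlation are assumptions. The weekly total is 300 × 960 waking minutes × 7 = 2,016,000.

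| Outcome (assumed mean; CV) | SE ratio | False positives, uncorrected Poisson |
|---|---|---|
| Average counts (300; 0.20 and 0.36) | 2.7–4.8 | 46–70% |
| CHAMPS kcal/wk (2,000; 0.4 and 0.8) | 13.6–25.9 | 89–93% |
| Weekly total counts (2,016,000; 0.36) | about 400 | 99.8% |

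Alternatives, range over all scenarios:
- gamma with log link: 3.8–6.7%
- log-scale ANCOVA: 3.5–6.0%
- Poisson with Pearson scale: 4.3–7.5%
- Poisson with robust variance: 5.7–9.0%
- planned t-test on change: 3.5–6.5%

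Simulation error is about ±1.8 points near 5% and about ±4 points near 50%.

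**Cross-check.** A correlation of 0.6 shrinks the residual SD by √(1 − 0.36) = 0.8. For mean 300 and CV 0.36 the ratio becomes 6.17 × 0.8 = 4.9 and the type I error 2[1 − Φ(1.96/4.9)] = 69%, in line with the simulation.

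**The case against.** A reader might infer that the primary PA comparison itself would turn out significant most of the time with no effect. The documents do not support that. The named primary analysis is the t-test on 6-month change; the GLM sentence follows the adjusted regression and is naturally read as its fallback. Poisson could not be fitted to change scores in any case, since they can be negative.

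A reader might also take Poisson to be the plan's fallback. It is one option to be considered, beside three transformations and gamma, and the log transformation and gamma held the error rate near 5% in the simulation. Nothing in the plan favours Poisson: the preliminary Actiwatch analysis and Aim 1 both use linear regression. Harm also requires a second step, fitting Poisson without a correction. The plan is silent on that rather than committed to it, and under Aim 2 it says a statistician will be consulted.

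Finally, the sizes are conditional. The SD of 107 comes from an osteoarthritis sample whose unit is given as average count per day. The means and the correlation are assumed, and the plan's further covariates could shrink the residual variance somewhat more. A wrong dispersion assumption also leaves the estimated arm ratio unchanged; only its standard error is affected.

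All of this stands and sets the limits of the point. It does not make plain Poisson acceptable for these outcomes. The unit dependence needs no assumed mean or SD, and consulting a statistician later does not pre-specify a choice.

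**Conclusion.** The point holds for the covariate-adjusted PA analysis under Hypothesis 2a. The plan names, without safeguard, an error model that does not suit any of its three PA measures. If it were chosen and fitted uncorrected, false-positive rates would be roughly 46–70% for average counts, about 90% for kcal per week and over 99% for weekly totals, given the assumed means, CVs and baseline correlation of 0.6. To call significance near-automatic would fit the last two measures but not average counts. The documents do not show that the Poisson option is likely to be used. This is a correction to a listed method; the trial's lead test is sound in this respect.

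**What to change.** Amend the sentence on non-normal data under Hypothesis 2a. Delete plain Poisson error for the PA measures, and keep the log transformation or gamma with log link, both already listed. If Poisson is retained, require an estimated scale (quasi-Poisson) or robust variance; at 28–35 per arm the estimated scale held the error rate slightly better (4.3–7.5% against 5.7–9.0%). State which option applies, and when, before outcomes are examined by arm. Because the log and gamma options need positive values, add how a zero score would be handled.

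The cost is a sentence or two in the analysis section, with no change to data collection, sample size or the primary t-test. Making ANCOVA with HC3 or bootstrap standard errors the default would be a matter of preference and is not needed.
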